5.5 Standardized questionnaires

Alcohol Use Disorders Identification Test (AUDIT) is a 10-item questionnaire with a simple scoring scale that will be administered during screening visit 1. A 3-item interim alcohol consumption (AUDIT-C) measuring consumption since that patient's last visit will be obtained during follow-up visits every 12 weeks (12, 24, 36, 48, 60, and 72) and the post-treatment visit (week 96) as part of the follow-up medical history.

Skinner Lifetime Drinking History is a detailed questionnaire that will be administered during screening visit 2.

Health Related Quality of Life (HRQOL, SF-36 version 2) is a 36-item, self-report measure designed to assess the quality of life in patients that will be administered during screening visit 2 and follow-up visits (24, 48, 72, and 96).

5.6 Drug dispensing

Drug dispensing would be done at the following visits: at randomization visit, and then every 12 weeks including week 12, 24, 36, 48, and 60 visits.

5.7 MRI exam purpose and rationale

The purpose of the MRI exam is to quantify the hepatic proton density fat fraction non-invasively in participants of the FLINT trial. The fat fraction is the proportion of mobile protons in liver tissue attributable to fat and thus is a non-invasive MR-based biomarker of liver triglyceride concentration.

To quantify the fat fraction, the MRI exam will use a fast spoiled gradient recalled echo (FSPGR) sequence that uses a low flip angle to reduce T1 bias, acquires multiple echoes after a single excitation to measure and correct for T2*decay, and uses spectral modeling to address fat-water and fat-fat signal interference effects. Using MR spectroscopy as the reference standard, the proposed MRI technique measures hepatic fat fraction accurately in human subjects at 1.5T or 3T and across different vendors. The technique provides high within-examination and between-examination precision. Linearity is maintained across the entire relevant biological range from <1% to >40% hepatic fat fraction. The technique is robust to minor variations in acquisition parameters, including those that may be encountered during usage in a clinical trial.

The FSPGR sequence proposed for imaging-based hepatic fat fraction quantification can be implemented on any up-to-date clinical scanner and thus can be used at all NASH CRN clinical centers with access to such a scanner. Moreover, the technique is imaging based and covers the whole liver, thus providing information on both the quantity and distribution of hepatic fat fraction. These characteristics represent critical advantages over the alternative technique of single-voxel proton MR spectroscopy to measure hepatic fat fraction in a multicenter clinical trial. While MR spectroscopy is currently considered the most accurate noninvasive technique to quantify hepatic PDFF,^{84, 85, 86, 87} it is not available at most NASH CRN clinical or satellite centers, and it is restricted in spatial coverage. The latter limitation may be problematic for reliable assessment longitudinal changes in hepatic fat content,^{88, 89} as is required by the FLINT trial.

Target population

The target population for the MRI exams will consist of eligible participants in the FLINT trial. Eligibility criteria for MRI examination are listed below:

- Inclusion: Willing and able to complete MRI examination procedures
- Exclusion:
 - A contraindication to MRI examinations
 - Extreme claustrophobia
 - Pregnant or trying to become pregnant
 - Weight or girth exceeds the scanner capabilities
 - Any condition or circumstance that, in the opinion of the site investigator, would interfere with completion of MR examinations

Safety screening

Clinical sites will screen subjects for MRI safety per institutional standards.

Exam scheduling

Subjects will undergo two MRI examinations. The first MRI exam will be performed after screening but prior to treatment randomization as contemporaneously as possible to, and no more than 90 days from the baseline biopsy. The second MRI exam will be performed as contemporaneously as possible to, and no more than 6 weeks before and no more than 12 weeks after the post-treatment biopsy. The goal will be to schedule the second MRI exam at the same or similar time of day as the first MRI exam. Clinical sites will determine the logistics of scheduling the MRI exam.

Pre-MRI exam instructions

Subjects will be instructed, if possible, to fast for 4 or more hours prior to the scheduled MRI exam but will be allowed to take necessary medications and small quantities of water.

Exam performance

Subjects will be positioned supine with a phased-array coil centered over the liver. After localizing sequences, an axial multi-echo-echo 2D FSPGR sequence will be performed through the liver. Imaging parameters will be selected as appropriate for 1.5T or 3T scanners. After completion of the exam, clinical sites will transfer MR images to the Radiology Reading Center (RRC). The RRC will be run through the Department of Radiology at University of California, San Diego.

Exam analysis

Image analysts at the RRC will review and analyze images. The analysts will place regions of interest in each hepatic segment. The fat fraction in each region of interest will be calculated using custom software developed by the RRC and validated in clinical patients and research subjects with liver fat fraction values ranging from <1% to >40%.^{90,91} The fat fraction in each region of interest will be recorded. The average fat fraction across segments will be calculated.

Data transmittal

The average hepatic fat fraction value calculated in each subject on each of the two MRI exams will be transmitted by the RRC to the Data Coordinating Center (DCC).

5.8 Liver biopsy

Liver biopsies will be performed 72 weeks after enrollment (window: 66-78 weeks) by the NASH CRN principal investigator designee. End-of-treatment liver biopsies will not be performed until the NIDDK program official has given approval to continue the FLINT trial based on safety and efficacy data obtained from the interim vanguard analysis.

Liver biopsies will generally be obtained from the right lobe of the liver using a 16G or larger biopsy

instrument. If the initial biopsy was obtained from the left lobe, then the 72 week biopsy must be obtained from the left lobe. Biopsies should be at least 1.5 cm in length.

5.9 Specimen repository

Specimens will be collected and stored at the NIDDK Biosample or Genetics Repositories for use as approved by the Steering Committee of the NASH CRN (see Appendix 9.3 for blood collection schedule). Specimens include serum, plasma, liver tissue, and DNA. The blood collected at screening and 12, 24, 36, 48, 60, 72, and 96 week visits will be centrifuged and divided into 0.5 mL aliquots of serum and plasma. Aliquots will be shipped to the NIDDK Biosample Repository and kept in a storage facility at -70 degrees C. When extra liver tissue is available, a portion of the liver biopsy specimen will be placed into 1 ml of RNAlater Solution within 1 to 5 minutes after biopsy. To prepare the samples for storage at -70 degrees C, the samples should incubate overnight at 4 degrees C to allow thorough penetration of the tissue, and then transferred to -70 degrees C until it is shipped to the NIDDK Biosample Repository on dry ice. If the patient has provided additional consent, blood will be collected during screening and shipped to the NIDDK Genetics Repository for extraction of DNA samples and stored at -20 degrees C.

5.10 Safety issues

Obeticholic acid

The latest version of the OCA Investigator's Brochure⁸³⁾ provides details about the safety profile of obeticholic acid obtained from clinical trials. This will be updated during the study as appropriate and in conformance with the appropriate FDA regulations. The investigators should be familiar with the safety profile of the drug.

To date the following AEs of note have been seen:

Normal Volunteers: Single doses up to 500 mg and multiple doses up to (and including) 250 mg (20 and 10x the dose used in this study, respectively) were administered. At the 100 mg daily dose, modest elevations in both ALT and AST were observed. At 250 mg, reversible elevations in ALT and AST (to a maximum of 5x ULN) were seen. Pruritus was experienced by half of the volunteers at 250 mg.

Primary Biliary Cirrhosis: In a 3 month, placebo controlled study in PBC patients evaluating 10 mg, 25 mg, and 50 mg of OCA pruritus was the only common AE clearly related to OCA use. The frequency of pruritus was higher at both the 25 mg and 50 mg doses and the severity of pruritus was worse in all 3 OCA treated groups (placebo group: 50%; OCA groups: 47-85%); 24% of the patients receiving 50 mg were discontinued from the study due to pruritus (which is the most common symptom in this cholestatic disease). Nausea (generally mild) was the only other AE seen in all three treatment groups more frequently than for placebo. Three patients at 50 mg had serious hepatic AEs (SAEs); two developed increases in bilirubin and liver enzymes which were considered likely related to OCA therapy. The other patient developed a bleed from previously existing esophageal varices. All of these patients recovered. The 50 mg dose is not considered a likely appropriate starting dose in cholestatic liver diseases. Subjects without severe pruritus at lower doses are likely to tolerate higher doses if titrated up.

Type 2 Diabetes Mellitus and NAFLD: A 6 week, placebo controlled study in patients with both diabetes and evidence of NAFLD was conducted with 25 and 50 mg doses. The drug was well tolerated. There were no AEs reported more frequently in more than 1 patient in the 25 mg group, except for palpitations (10%), compared to the placebo group. At 50 mg, only constipation (24%) and nausea (14%), both generally mild, were reported more frequently, compared to the placebo group. Constipation was not seen more frequently in the treated patients in the PBC study and was not expected as mild diarrhea is a common AE seen with CDCA administration. Further studies are needed to determine if constipation, or

other AEs, are associated with OCA therapy.

Placebo

Currently, there are no FDA approved therapies for NASH. Therefore, use of a placebo is justified for comparison of efficacy with obeticholic acid. Previous studies have shown that patients in NASH studies improve even on placebo,⁷⁶ and the response rate in the PIVENS trial was 19% in the placebo-arm. These improvements are related to several factors including Hawthorne effect leading to lifestyle changes, and sampling variability. If patients on placebo develop hypertension, or any other metabolic disease, they would receive standard of care treatment by their PCP. The risk of progression of NASH over a 96 week period is minimal based upon the PIVENS trial. Therefore, the placebo-arm is justifiably needed.

Management of adverse events

- During the trial if a patient develops side effects thought to be due to the study medication and requires cessation of the study medication, then the medication will be stopped for 4 weeks. If the side effects disappear, an attempt will be made to reintroduce the study medication after 4 weeks. If the symptoms reappear, the study medication will be stopped and the patient will no longer receive the study medication, but will continue to be followed in the trial according to the protocol, in keeping with the “intention-to-treat” paradigm.

MRI

MRI is a minimal risk procedure if standard precautions and practice are exercised. Standard precautions for MRI procedures include: claustrophobia, anxiety, discomfort from lying supine for 30 minutes, hearing loss, and heating of metal in the body. Patients will be screened by questionnaire and excluded when the presence of metal is known or suspected. Sources of metal include the presence of a cardiac pacemaker or defibrillator; metal fragments in eyes, skin, body; heart valve replacement, brain clips, venous umbrella; being a sheet-metal worker or welder; aneurysm surgery, intracranial bypass, renal, aortic clips; prosthetic devices such as middle ear, eye, joint or penile implants, joint replacements; hearing aid, neurostimulator, insulin pump; intrauterine device; shunts/stents, metal mesh/coil implants; metal plate/pin/screws/wires, or any other metal implants; permanent eyeliner, eyebrows.

Liver biopsy

Patients will have up to two liver biopsies for research purposes during their participation in this protocol. About 20% of people who have a liver biopsy have some degree of pain over the liver that may last a few minutes up to several hours. This occasionally requires pain medication and usually disappears completely within a day or two. A rare complication of liver biopsy is severe bleeding such that a blood transfusion or even radiological/surgical interventions are required to stop the bleeding (less than 1 in 1,000). Very rarely (less than 1 in 10,000 reported cases) death has occurred from bleeding after a biopsy. We intend to minimize the risks associated with liver biopsy (a) by requiring that each of the physicians who will obtain liver biopsies in the NASH CRN be very experienced in safely obtaining the liver biopsy specimens, (b) by not enrolling subjects with cirrhosis or subjects with coagulopathy, (c) by adhering to the good clinical practice in performing the liver biopsy, (d) by assuring that an attending hepatologist or radiologist directly supervises if a physician trainee is performing the procedure, and (e) by considering a transjugular liver biopsy in morbidly obese patients in whom a percutaneous, mid-axillary approach may not be feasible.

Patient privacy

It is the investigator’s responsibility to conduct the protocol under the current version of the Declaration of Helsinki, Good Clinical Practice, and rules of local IRBs. The investigator must ensure that the patient’s anonymity be maintained in their data submission to the Data Coordinating Center. Patients will be identified only by an identification code but not by their name, SSN, or hospital medical record number. Investigators will maintain a separate confidential enrollment log which matches identifying

codes with the patients' names and addresses (i.e., available only to local clinic staff). All study material will be maintained in strict confidence.

Specimen repository

It is anticipated that serum, plasma, DNA, and liver tissue from the participants will be stored for future studies related to NASH and possibly other liver/metabolic diseases. These samples will be stored at the NIDDK Biosample Repository and NIDDK Genetics Repository. The NASH CRN Steering Committee will develop specific guidelines addressing the issues such as (a) obtaining a separate informed consent, (b) storage, (c) transportation of the material, (d) who will have access to the material, and (e) what investigations will be conducted.

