5.12 Management of concomitant conditions

Hypertension, hyperlipidemia and diabetes will be managed in conjunction with the patient's primary care physician according to the protocols described in the Standard of Care document prepared by the Standard of Care Committee of the NASH CRN. Pregnancy will be managed according to the guidelines described in section 5.15.

In the event of major dermatological reactions such as generalized urticaria, bullous rashes, exfoliative dermatitis, or Stevens-Johnson Syndrome, study medication will be discontinued immediately and not restarted. For local skin reactions, study medication may be discontinued if the skin reactions are potentially drug related. If the rashes clear, the study medication may be restarted.

If local skin reactions recur with restarting the study medication, study medication should be discontinued. In cases where the study medication has been discontinued, the study medication will be unmasked and the participant, investigator, and the primary care provider will be notified in order to prevent future exposures.

6. Adverse event monitoring and reporting

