6.5 Procedures for unmasking treatment assignment

Treatment assignments are double masked throughout the study until all data collection for the trial has been completed and the database of trial data is officially “locked” for analysis (i.e., after completion of the 24 week post trial follow-up for all patients and entry of all data). Every effort will be made to maintain the masking throughout the study except in emergency situations. The code of specific pharmacological treatment will not be broken without the knowledge of the clinical center’s principal investigator.

In unforeseen situations where the clinical center principal investigator considers unmasking is in the best interest of the participant’s health and well-being, unmasking may be performed. In such circumstances, the NASH CRN Executive Committee will be notified within one working day. Unmasking of study medication may occur under the following conditions:

Severe allergic reaction (Stevens-Johnson Syndrome): Study medication is stopped indefinitely. The patient, primary care provider (PCP), local principal investigator and pharmaceutical manufacturer may be unmasked.

Pregnancy during the study: Study medication will be stopped indefinitely, and the coded medication will be unmasked. The patient, PCP, and investigator may be notified of the assigned treatment and the associated risks of teratogenicity.

The Data and Safety Monitoring Board will review all instances of unmasking that occur.

7. Statistical design and analysis

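### Section 5.10 directs rechallenge once any drug-attributed side effect has cleared, with no exception for the major skin reactions after which 5.12 (and 6.5, for Stevens-Johnson Syndrome) forbids it

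*Protocol*

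**What the plan says.** Three places in the protocol govern stopping and restarting study drug after a reaction.

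- **Section 5.10, under management of adverse events.** The rule applies to "side effects thought to be due to the study medication and requires cessation of the study medication". Drug is withheld for 4 weeks, and then: "If the side effects disappear, an attempt will be made to reintroduce the study medication after 4 weeks". In this rule, a permanent stop comes only if the symptoms return after reintroduction.
- **Section 5.12, management of concomitant conditions.** For major dermatological reactions, of which it gives four examples, the text reads: "generalized urticaria, bullous rashes, exfoliative dermatitis, or Stevens-Johnson Syndrome, study medication will be discontinued immediately and not restarted". Local skin reactions are treated differently: "If the rashes clear, the study medication may be restarted". For cases in which drug was stopped, the section adds: "the study medication will be unmasked and the participant, investigator, and the primary care provider will be notified in order to prevent future exposures".
- **Section 6.5, on unmasking.** "Severe allergic reaction (Stevens-Johnson Syndrome): Study medication is stopped indefinitely". It also says: "The Data and Safety Monitoring Board will review all instances of unmasking that occur".

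**The concern.** Section 5.10 is the place where site staff would look for what to do about a drug reaction, and its wording is directive. It does not limit the rule by type or severity of reaction, and it does not point to 5.12 or 6.5. The prohibition on restarting sits under a heading about concomitant conditions, which is a less obvious place to search for a drug reaction.

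What is at stake is patient safety. Someone following 5.10 alone would be told to try the drug again after a severe skin reaction that another section says must end treatment for good.

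**Working it through.** There is no figure to reproduce; the check compares the three provisions.

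| | 5.10 | 5.12 | 6.5 |
|---|---|---|---|
| Trigger | Any side effect thought due to study drug that requires stopping it | Major dermatological reactions (four examples, Stevens-Johnson Syndrome among them) | Severe allergic reaction, with Stevens-Johnson Syndrome named |
| Depends on attribution to drug? | Yes | Not as worded, for major reactions | Not as worded |
| Stop | 4 weeks | Immediate | Indefinite |
| Restart | Directed, if the effects have disappeared | Forbidden | None |
| Exception stated | None | Separate rule for local reactions | None |
| Refers to the other two sections? | No | No | No |

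**Step 1: when do 5.10 and 5.12 both apply?** The reaction must be a major dermatological one (5.12), it must be thought due to study drug (5.10), it must require stopping the drug (5.10; met automatically, because 5.12 orders the stop), and it must have disappeared (5.10's condition for reintroduction). A major skin reaction not attributed to drug is outside 5.10, and one that persists does not meet 5.10's condition. Neither produces a conflict.

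**Step 2: can both be followed in the overlap?** No. Section 5.10 says an attempt at reintroduction will be made; 5.12 says the drug is not restarted.

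**Step 3: how far does 6.5 extend the conflict?** Of the four reactions named in 5.12, 6.5 names one, Stevens-Johnson Syndrome. For that reaction 5.10 conflicts with both sections; for the other three it conflicts with 5.12 only. The other indefinite stop in 6.5 is for pregnancy, which is not a drug side effect and so is outside the 5.10 rule.

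**Step 4: is the 5.12 prohibition deliberate?** It appears so. The same section allows restart after local reactions that clear, which separates the two tiers on purpose. Section 5.10 does not reflect that distinction. There is also a smaller mismatch for local reactions: 5.12 makes restart optional and sets no interval, while 5.10 makes the attempt directive after 4 weeks.

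**Step 5: does the protocol settle which rule prevails?** No section states an order of precedence, and none of the three refers to another.

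**The case against.** The strongest reply is that a specific rule overrides a general one. Section 5.10 is a one-bullet default that follows an account of mainly tolerability effects such as pruritus, nausea and constipation, with no major skin reaction among them. Its language of symptoms reappearing after an attempt at reintroduction suits a temporary hold. Section 5.12 deals with skin reactions by name, and 6.5 agrees with it on Stevens-Johnson Syndrome. The stated purpose of unmasking in 5.12, to prevent future exposure, cannot be squared with rechallenge, and the DSMB reviews every unmasking. On this view all that is missing is a cross-reference.

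Most of this stands. It is how an experienced investigator would resolve the texts, and it is why re-exposure is unlikely. It does not remove the inconsistency, for two reasons. The precedence is supplied by the reader and not by the protocol. And the safeguards take effect only once 5.12 has been applied: someone working from 5.10 meets no unmasking step, and DSMB review of unmaskings is not described as a check before rechallenge.

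A reader might go further and infer that the protocol as a whole exposes patients to rechallenge after severe skin reactions. The documents do not support that, because the two sections that address such reactions by name both prohibit restart. Nor does 6.5 contradict 5.10 for every reaction listed in 5.12; it names only Stevens-Johnson Syndrome.

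**Conclusion.** The inconsistency is real and minor. It arises only for a major dermatological reaction that is attributed to study drug and has disappeared by the time 5.10 calls for reintroduction. In that case 5.10 and 5.12 give opposite instructions, and for Stevens-Johnson Syndrome 6.5 also opposes 5.10. The conclusion rests on reading 5.10 literally, as a rule without exceptions, which is how it is written.

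There is no effect on power, error rates or the primary analysis. A reader might want a count of patients at risk, but the protocol gives no rate for such reactions and no rate at which they clear, so any count would be a guess.

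Section 5.12 also contains a faulty reference: "Pregnancy will be managed according to the guidelines described in section 5.15", although section 5 ends at 5.12. That is a separate clerical slip. It concerns pregnancy and adds no weight to this point.

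**What to change.** Add an exception to the 5.10 bullet, for example: *except for major dermatological reactions (section 5.12), including Stevens-Johnson Syndrome (section 6.5), after which study medication is permanently stopped and not reintroduced; local skin reactions are managed under section 5.12*. This states the precedence where staff will look for it, and its last part also removes the smaller mismatch over local reactions.

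The cost is one clause, with no effect on data collection, sample size or analysis.

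Separately, the sponsor should correct the reference to section 5.15 when the text is next edited. Section 6.5 does contain stopping and unmasking rules for pregnancy, but the protocol does not show whether that is the intended target, so the sponsor needs to confirm it.
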